## **8.2 Laboratory Evaluations**

### **8.2.1 Clinical Laboratory Evaluations**

During the initial session, all participants will be asked to participate in a urine drug screen in order to help screen out any individuals who have a drug use problem. A urine pregnancy test will also be performed for any female participant who is unable to confirm pregnancy status. This information will be recorded on the inclusion/exclusion criteria checklist (*Appendix M*) to be completed by the researcher. Participants will also be asked to complete a drug urine test during the initial session to verify drug use status.

## 8.2.2 Special Assays or Procedures

The Brief Assessment of Cognition in Schizophrenia (BACS) (*Attachment 12*) will be administered during the 1st day of stimulation, the 5th day of stimulation and at the one month follow-up. This assay was specifically designed to assess cognition in patients diagnosed with schizophrenia and will be used to obtain a baseline assessment of cognition in each participant. We will also be using this assay as a safety monitor and data collection tool throughout the study to assess any changes in cognition that may be seen as a result of the treatment.

There will be two procedures used throughout this study. Each participant will attend 5 consecutive weekdays of stimulation for this study. Each participant will be randomly assigned to one of three treatment arms for this study (sham, 10HZ tACS or 2mA tDCS). Electrodes with a measurement of 5x5cm will be placed between Fp1 and F3 and between T3 and P3, and a return electrode, 5x7cm, will be placed over Cz. In order to detect any change(s) at the neurophysiological level, an EEG will be performed during the 1st day of stimulation, the 5th day of stimulation, and at the one month follow up session. This measurement will contribute to the design of novel network-level biomarkers of schizophrenia and of treatment response.

In addition to the above procedures, we will be collecting a saliva sample at the initial visit. This sample will be used to test for a single nucleotide polymorphism in the BDNF gene whose presence may have an influence on efficacy of brain stimulation. Within the central nervous system, BDNF regulates survival, proliferation, and synaptic growth as well as directly influences synaptic plasticity in the adult human brain (Antal et al. 2010). Egan et al. (2003) demonstrated that Val66Met, a single nucleotide polymorphism in the BDNF gene, has functional consequences in healthy humans including decreased episodic memory and hippocampal inducing a reduction in recall capacity. This polymorphism is common in over one third of the Caucasian population (65% Val66Val to 35% Val66MET) (Pezawas et al. 2004; Hariri and Weinberger 2003). Kleim et al. (2006) found that individuals with the Val/Val polymorphism respond to tDCS and transcranial magnetic stimulation treatments (TMS) with expected changes whereas individuals expressing the Val/MET allele do not. These authors indicate the difference to be caused by the impairment in synaptic plasticity caused by the Val/MET allele. These findings suggest that individual of treatments using brain stimulation may be partially genetically predetermined and should be taken into account when performing such procedures. Accordingly, we will conduct genotyping of all participants in this study in order to assess BDNF status. We will perform exploratory analyses in which we group participants by BDNF status.

## 9 ASSESSMENT OF SAFETY

### 9.1 Specification of Safety Parameters

There will be three different assessments used to ensure participant safety. First, vitals will be recorded at the beginning of each session. This assessment is used to monitor any physiological changes.

A Positive and Negative Syndrome Scale will be administered before the first stimulation session and on the last day of stimulation as well as at the one month follow up. This tool is used to assess any changes in symptoms associated with this disorder. We do not expect any changes in these symptoms; additionally we did not find any changes in a related clinical trial (IRB# 13-2995). Should there be a significant change in PANSS rating scores, (>25% increase) we will direct the participant to [name] or [name] for further follow up and file a AE report.

After each stimulation session, a stimulation adverse effects questionnaire (*Attachment 1* and *Attachment 2*) will be administered. This tool is used to document any side effects experienced during stimulation. The researcher will also check with the participant throughout the 20 minute stimulation sessions to make certain no discomfort is felt. The stimulation session will be terminated if the participant reports having unmanageable discomfort or pain (more than “moderate”). Additionally, this information will be reported on an AE report form (*Appendix B*) and an AE log (*Appendix C*).

### 9.2 Methods and Timing for Assessing, Recording, and Analyzing Safety Parameters

#### 9.2.1 Adverse Events

**Adverse Event:** An AE, as defined by the NIH, is any unfavorable changes in health, including /abnormal laboratory findings that occur in trial participants during the clinical trial or within a specified period following the trial.

All AEs including local and systemic reactions not meeting the criteria for “serious adverse events” will be captured on the appropriate CRF. In addition, the AE Report Form will be completed by the study coordinator (*Appendix B*). The AE report form includes the follow; what is known about the therapy and previous reported side effects, if the AE occurred in temporal relation to the therapy, whether or not the AE improves or disappears when treatment is stopped, whether the AE is a worsening of baseline

symptoms or related to a concurrent medical condition or medication use. Once complete, this form will be given to the PI and the Co-I who will review, comment and sign this form. Completed forms will be placed in the participant's folder.

The study coordinator will document any AE occurrence on the AE log (*Appendix C*) which includes information such as the date of the AE, severity, relationship to the treatment (assessed by the PI), actions taken, and outcome(s). The log will be reviewed and initialed by the PI 72 hours after being completed. All AEs occurring during the clinical trial will be documented appropriately regardless of relationship to tACS. All AEs will be followed to adequate resolution and will be graded for severity and relationship to the study treatment. Any medical condition noted at the initial session will be considered as baseline and not reported as an AE.

All AEs will be graded for severity using the following guidelines.

- **Asymptomatic:** the participant is exhibiting no symptoms due to the event; no treatment needed.
- **Mild** Adverse Event– Event results in mild or transient discomfort, not requiring intervention or treatment; does not limit or interfere with daily activities (e.g., insomnia, mild headache).
- **Moderate** Adverse Event – Event is sufficiently discomforting so as to limit or interfere with daily activities; may require interventional treatment (e.g., fever requiring antipyretic medication). In the case of a moderate adverse event the medical advisor may recommend an over the counter medication.
- **Severe and undesirable** Adverse Event – Event results in significant symptoms that prevents normal daily activities; may require hospitalization or invasive intervention (e.g., anemia resulting in blood transfusion).

Changes in the severity of an AE will be documented with the Note to File document (*Appendix N*) and will be filed in the participant's folder.

**Relationship to Study Products:** The PI and Co-I will together determine whether an AE is associated with the study treatment. The event will be labeled associated if the event is temporally related to the administration of the therapy and no other factors can explain the event. The event will be labeled as not associated if the event is temporally independent of the study treatment and can be explained by external factors such as major life events.

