*Risk of Injury and Discomfort:* Transcranial current stimulation has been used without any reports of serious side-effects for more than a decade. This stimulation mode has NOTHING to do with electroconvulsive therapy that applies many orders of magnitude higher stimulation current. Rather, transcranial current stimulation is so weak that it does not cause super-threshold activation of neurons ([name] and McCormick, 2010). In particular, tACS has been used without reports of any serious side-effects. Some participants report a transient mild tingling, burning, or itching underneath the electrodes and headache, but no other side effects have been noted. Importantly, it remains unclear

if these mild side-effects were caused by the transcranial brain stimulation. In order to monitor these side-effects, we will be administering an adverse effects stimulation questionnaire (*Attachments 1 &2*) after each stimulation session to determine whether these effects were experienced. Research personnel present during these sessions will also check in with the participant periodically during the stimulation to see whether they are comfortable. If any side-effect occurs (rated by the participant as stronger than “moderate”) or the participant is experiencing severe discomfort, the stimulation will be immediately stopped.

While not previously reported with tDCS or tACS in humans, there is a theoretical possibility that stimulation of neuronal circuits could lead to epileptic discharges. To minimize this occurrence, we screen and exclude patients with personal and family history of neurological conditions from the study. If abnormalities or a seizure is witnessed during the course of the study, the subject will be referred to a neurology clinic for further evaluation and treatment.

We have no evidence that our treatment paradigms will increase auditory hallucinations if not treated (receive the sham treatment), as participants, will be by definition, stable. If an enrolled patient shows signs of increase symptoms that were not apparent during enrollment, a referral to UNC Psychiatry will be made. [name], Co-I, will facilitate this process.

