## **7.4 Follow-up**

### **One week Follow-up Visit (Visit 10, one week after last day of stimulation)**

Upon participant arrival, vital signs will be taken and documented. An EEG will then be administered. The EEG recording will include resting state data along with two auditory tasks, and the EEG Questionnaire will be administered. The AHRS will then be administered to assess severity of auditory hallucinations. Each participant will be asked whether they believe their symptoms have improved (*Attachment 11*). Participants will be paid at the conclusion of this study visit.

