### **14.3 Types of Data**

Data will be collected to determine eligibility. During the initial session, the SCID, AHRS, PANSS, CGI-S, SAS and AIMS will be administered. In order to participate in this study, the participant must have a diagnosis of schizophrenia or schizoaffective disorder, experience medication refractory auditory hallucinations, and are currently not committed in an inpatient hospital and on stable medication.

We will also be collecting data to assess cognitive abilities at the 1st day of stimulation, the 5th day of stimulation and end point (one month follow-up). The BACS will be used to assess cognition in each participant and will be used as a safety monitor and data collection tool to

monitor any changes throughout the course of the study.

The stimulation adverse effects questionnaire will be administered after each stimulation in order to monitor any side effects the participant may experience from the stimulation treatment. After the last stimulation and at the one week and one month follow-up, participants will be asked whether they believe their symptoms have improved due to treatment.

The AHRS will be our primary outcome for this study. We will administer this questionnaire at the initial session, on the 1st day of stimulation, the 5th day of stimulation, and the one week and one month follow up. As our primary outcome, the data we collect with the AHRS will be used to determine efficacy of treatment.

The PANSS, the CGI-S, the SAS and the AIMS will be used to collect additional data throughout the study. This questionnaire will also be administered on the 1st day of stimulation, the 5th day of stimulation, and the one week and one month follow up, in addition to during the initial session.

An EEG recording will be performed at the 1st day of stimulation, the 5th day of stimulation, and at the one week and one month follow-up. The data collected from the EEG recording will enable assessment of neurophysiological changes induced by stimulation.

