## APPENDIX B: AE REPORT FORM

## Adverse Effects Report:

*Reasons for Report (adverse event, time, date and place of occurrence if available):*

1. What do we already know about the therapy?
  - a.
2. What is the temporal relationship of the AE to the study therapy?
  - a.
3. Does the AE improve or disappear when the therapy is stopped?
  - a.
4. Is the AE a worsening of baseline symptom(s)?
  - a.
5. Is the AE a result of an underlying concurrent medical condition(s) or concurrent medication(s)?
  - a.
6. Additional Information provided by research team
  - a.

Research team member signature \_\_\_\_\_

Date

---

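### The baseline-condition rule in 9.2.1 has no exception for worsening and conflicts with the protocol's own AE definition, AE form and PANSS trigger, so aggravated hallucinations may be logged inconsistently

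*Combined protocol and SAP*

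**What the plan says.** - Section 9.2.1 defines an AE as "any unfavorable changes in health, including /abnormal laboratory findings that occur in trial participants during the clinical trial" or in a set period afterwards, and has every AE documented whatever its relationship to treatment.
- The same section says that the AE report form captures "whether the AE is a worsening of baseline" symptoms. Item 4 of the form in Appendix B asks the question directly: "Is the AE a worsening of baseline symptom(s)?"
- The same section then gives the rule at issue: "Any medical condition noted at the initial session will be considered as baseline and not reported as an AE". Nothing in that sentence or after it deals with a baseline condition that worsens.
- Section 9.1 names three safety assessments: vital signs, the PANSS and the stimulation adverse effects questionnaire. For the PANSS it says "Should there be a significant change in PANSS rating scores, (>25% increase)", the participant is directed to a named clinician and an AE report is filed. The AHRS is not among the three.
- Section 7.4, for the one-week visit, says "The AHRS will then be administered to assess severity of auditory hallucinations". It schedules no PANSS and no adverse effects questionnaire.
- Section 14.3 places the PANSS on Days 1 and 5 of stimulation "and the one week and one month follow up, in addition to during the initial session".
- Section 2.3.1 provides a psychiatric referral: "If an enrolled patient shows signs of increase symptoms that were not apparent during enrollment". It does not mention an AE record.

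**The concern.** Auditory hallucinations are both the symptom being treated and the basis of the primary outcome. Their aggravation under active stimulation is therefore among the harms that matter most here. The one sentence on how pre-existing conditions are reported would, if followed to the letter, keep that harm out of the AE record.

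Under 9.6, what the DSMB sees every 6 months is AE reports, and the reasons for stopping listed there are cognitive decline and seizure. AE classification is thus the stated path by which worsening symptoms would reach the DSMB. If one coordinator follows the baseline sentence and another follows the definition and the form, the same clinical change is an AE for one participant and not for the next. A comparison of AEs across three arms of 16 has little room for that kind of noise.

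**Working it through.** No sample size, error rate or event count bears on this point, so the check is a cross-reading of the provisions.

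**1. Who falls under the sentence.** Section 5.1 requires at least 3 auditory hallucinations per week, and 7.2 scores the AHRS at the initial visit. The symptom is therefore noted at that session in every randomised participant: 3 arms × 16 = 48 of 48.

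**2. One case under each provision.** Suppose hallucinations are more severe after stimulation than at the initial session.

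| Provision | Result |
|---|---|
| 9.2.1, baseline sentence | Not reported as an AE |
| 9.2.1, AE definition | An AE: an unfavourable change in health during the trial |
| 9.2.1, form description; Appendix B item 4 | Presupposes that worsening of a baseline symptom can be an AE |
| 9.1, PANSS rule | AE report required if the PANSS rises more than 25% |

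The first row cannot be squared with the others. The conflict with 9.1 is the sharpest. A rise on a schizophrenia symptom scale, in people whose schizophrenia or schizoaffective disorder was confirmed at the initial session, is worsening of a condition noted then. 9.1 requires an AE report; 9.2.1, taken literally, forbids one.

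**3. Whether the form resolves it.** The form is completed for events already regarded as AEs. Item 4 describes such an event; it does not decide whether one is recorded. It shows what the authors probably intended but does not override the baseline sentence.

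**4. Which instruments could pick up worsening, by visit.**

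| Visit | AHRS | PANSS | Adverse effects questionnaire |
|---|---|---|---|
| Day 5 | Yes | Yes | Yes |
| One week | Yes | Not in 7.4, 9.1 or Appendix A; yes in 14.3 | Not in 7.4 or Appendix A; yes in 14.4 |
| One month | Yes | Yes | Yes in 7.5 and 14.4; not marked in Appendix A |

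The PANSS rule can operate at 2 of 3 post-treatment visits according to 7.3 to 7.5, 9.1 and Appendix A, or at 3 of 3 according to 14.3. The AHRS is taken at 3 of 3, but no section says that an increase in it is, or should be considered for, an AE.

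**5. The referral sentence in 2.3.1.** Its closing qualifier can attach to the symptoms (new symptoms only, which leaves out hallucinations) or to the increase (any increase not seen at enrolment, which includes them). The preceding sentence concerns an increase in hallucinations, which favours the second reading, but the wording allows both.

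**The case against.** The best defence is that 9.2.1 should be read as a whole. The definition is broad, the form asks about worsening, and the baseline sentence serves only to stop pre-existing conditions being entered as new events. One can add that Appendix B separates baseline symptoms (item 4) from concurrent medical conditions (item 5), so the phrase in the baseline sentence may have been meant for comorbidities. Both readings are reasonable and may be what was intended. Neither is written down, and the sentence applies to any medical condition without defining the term.

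A reader might also infer that worsening hallucinations are never AEs, that the PANSS is the only way to an AE report, or that a worsening at one week has no route at all. The documents do not support these stronger readings:

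- 9.1 does not call the PANSS rule exclusive.
- The general AE route (9.2.1) and the serious AE route, which includes hospitalisation (9.2.3), carry no PANSS condition.
- 14.4 puts the adverse effects questionnaire at each follow-up, and 14.3 puts the PANSS at one week. The visit descriptions disagree, but the assessments cannot be assumed absent. The questionnaires themselves are in attachments not available here, so it cannot be said that they miss worsening.
- The PI's weekly look at the data (section 14 and 14.4) is not confined to the AE log, and participants are asked at one month whether symptoms are better, worse or unchanged (7.5).

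Finally, it is tempting to turn the 20% AHRS stability margin used at screening into an AE threshold. That margin is an eligibility rule. On assumed scores, it is exceeded by a 2-point rise from 5 (5 × 1.2 = 6, so 7) and by a 5-point rise from 22 (22 × 1.2 = 26.4, so 27). The protocol offers nothing to justify it as a safety limit.

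**Conclusion.** The point holds as an internal contradiction with a practical consequence. Read literally, the baseline sentence excludes aggravation of a symptom that all 48 participants have at entry. It conflicts with the AE definition, the AE form and the PANSS trigger. The AHRS, taken at all three post-treatment visits, has no stated link to an AE record.

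The consequence is possible inconsistent logging and possible absence from the AE reports sent to the DSMB, not loss of the data: AHRS scores are kept as outcome data and compared by arm. How many events would be affected cannot be estimated, because the documents give no baseline AHRS values and no expected rate of worsening. The conclusion assumes that at least some staff would apply the sentence as written and would count hallucinations as a noted medical condition. The sentence should be corrected. The primary efficacy analysis does not depend on it.

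**What to change.** 1. In 9.2.1, amend the sentence so that a condition noted at the initial session is not an AE unless it increases in severity or frequency after the first stimulation, in which case it is recorded as one. This brings it into line with the definition and with Appendix B item 4.
2. In 9.1, state that the AHRS scores already collected at Day 5, one week and one month are reviewed for such worsening. Any numerical threshold is for the sponsor to set and justify.
3. Reconcile 7.4, 9.1, 14.3, 14.4 and Appendix A on whether the PANSS and the adverse effects questionnaire are given at one week, and make Appendix A agree with 7.5 on the questionnaire at one month.
4. Clarify which symptom increases the referral sentence in 2.3.1 covers.

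Items 1 and 2 take a clause and a sentence and need no new assessments. The cost is some extra AE entries that reflect ordinary fluctuation. These are recording and consistency changes only; no rule for care, referral or stopping is proposed.

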## 9.2.2 Expected Adverse Reactions

Transcranial current stimulation has been used without reports of any serious side-effects. Some subjects report a transient mild tingling, burning, or itching underneath the electrodes and headache, but no other side effects have been noted. Importantly, it remains unclear if these mild side effects were caused by the transcranial brain stimulation. During the stimulation, the researcher will ask the participant about their comfort. Stimulation will immediately be stopped if any discomfort (more than “moderate”) is reported. In theory, there is a possibility that application of weak stimulation current could induce a seizure.

These adverse reactions will be monitored with the stimulation adverse effects questionnaire (*Attachment 1 and Attachment 2*). The following scale reflects the scoring of severity for any possible side effects.

- 1 = Absence of the indicated symptom
- 2 = Mild (awareness of a symptom but the symptom is easily tolerated)
- 3 = Moderate (discomfort enough to cause the researcher to be informed)
- 4 = Severe (incapacitating; the stimulation is terminated due to extreme discomfort)

All expected adverse reactions questionnaires are a daily source document that will be placed in each individual’s folder. Should the DSMB ask to see a complete report of this information a report can be regenerated for their viewing.

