## **9.6 Safety Oversight**

Safety oversight will be under the direction of a DSMB composed of [name], an epidemiologist, a biostatistician and one or more clinical researchers. The DSMB will review AEs every 6 months whereas the medical monitor will review AEs in real time and make decisions as to each participant's continuation in the trial. The PI will review AEs weekly with research team and may request additional review by Co-I on a case-by-case basis. The medical monitor will also be present at weekly meetings in order to discuss/explain any event(s) that may occur.

Every 6 months DSMB will review blinded AE reports. If there is reason to view unblinded information, the DSMB will directly receive the list of participants' identification numbers from a [name] Lab member, not otherwise associated with this clinical trial. Participant identification number will be displayed in a table according to the three arms of the study; however the specific treatment of that arm will not be disclosed. This will allow the DSMB to compare the three treatment groups.

Reasons for stopping the study and asking for further investigation include; decrease in cognitive abilities based on baseline and end of study data (>25% decrease in scores in 2/10 of the first participants or 20% of participants overall.). In addition, as mentioned above, if a seizure occurs during a study visit, the clinical trial will be temporarily be placed on hold for further investigation.

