### **14.2 Data Capture Methods**

Clinical data (including AEs, concomitant medications, and expected adverse reactions data) and clinical laboratory data will be entered into a data capture system provided by REDCap. The data system includes password protection and internal quality checks, such as automatic range checks, to identify data that appear inconsistent, incomplete, or inaccurate. Clinical data will be entered directly from the source documents.

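### The protocol does not say which questionnaire-rated stimulation reactions become adverse events, and no scheduled DSMB review compares the by-session ratings by arm

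*Combined protocol and SAP*

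**What the plan says.** Three sections deal with recording.

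- **Section 9.2.1** is the general rule: "All AEs including local and systemic reactions not meeting the criteria for" a serious event go on the CRF, with an AE Report Form and a line in the AE log. The lowest symptomatic grade, mild, is defined as "Event results in mild or transient discomfort, not requiring intervention or treatment", and a mild headache is one of its examples.
- **Section 9.1** describes the post-session questionnaire, says that a session ends if discomfort exceeds moderate, and continues: "Additionally, this information will be reported on an AE report form" and in the AE log.
- **Section 9.2.2** lists headache and slight skin sensations under the electrodes as expected reactions and gives the questionnaire scale (1 absent, 2 mild, 3 moderate, 4 severe). It then says: "All expected adverse reactions questionnaires are a daily source document that will be placed in each" participant's folder. AE forms and the AE log are not mentioned there.

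On oversight, Section 9.6 provides that "Every 6 months DSMB will review blinded AE reports". The questionnaire data come under a separate arrangement in Section 9.2.2: "Should the DSMB ask to see a complete report of this information a report can be regenerated for their viewing". The view by arm in Section 9.6 is conditional: "If there is reason to view unblinded information, the DSMB will directly receive the list of" participant identifiers, grouped into three arms whose treatments are not named.

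Section 14.2 puts the ratings in REDCap: "Clinical data (including AEs, concomitant medications, and expected adverse reactions data) and clinical laboratory data will be entered into a data capture system".

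**The concern.** The questionnaire is the only harm measure taken after every session in every arm, so it is the natural basis for comparing the tolerability of sham, tACS and tDCS. Two things weaken it.

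First, a participant who scores a headache 2 or 3 has an AE under Section 9.2.1, may not have one under Section 9.1, and has a filed source document under Section 9.2.2. If staff apply different sections, AE counts reflect recording habits as well as reactions.

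Second, the DSMB's routine material is AE reports without arm labels. The ratings that would show an excess in one arm are outside that material unless the board requests them, and the split by arm needs a reason that the protocol does not define. Section 11.3 plans no analysis of the ratings, so the final analysis does not make the comparison either.

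**Working it through.** The plan gives no figure on this point to reproduce. The check is mainly a reading of the sections side by side.

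**1. What happens to each questionnaire score**

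| Score | Section 9.2.1 | Section 9.1, threshold reading | Section 9.1, broad reading | Section 9.2.2 |
|---|---|---|---|---|
| 2 (mild) | AE form and log | no entry required | AE form and log | folder; AE status not stated |
| 3 (moderate) | AE form and log | no entry required | AE form and log | folder; AE status not stated |
| 4 (severe) | AE form and log | AE form and log | AE form and log | folder; AE status not stated |

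The two readings of Section 9.1 turn on what its closing reference to the information covers: the discomfort above moderate just described, or all questionnaire results. Score 4 is an AE on every reading. Scores 2 and 3 are not settled.

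**2. The severity scales do not map.** Moderate on the questionnaire (Section 9.2.2) means discomfort worth telling the researcher about. Moderate on the AE scale (Section 9.2.1) requires an effect on everyday functioning. A score of 3 therefore cannot simply be carried over as a moderate AE.

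**3. Who sees the ratings, and by arm or not**

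- DSMB every six months (Section 9.6): AE reports, blinded.
- DSMB on request (Section 9.2.2): complete questionnaire report.
- DSMB if there is a reason (Section 9.6): masked arms, no trigger defined.
- Investigator, weekly (Sections 9.6 and 14.4): AEs and unusual activity, in a double-blind trial (Section 5.4), so not by arm.
- Final analysis (Section 11.3): EEG alpha power, AHRS, PANSS and BACS; not the questionnaire.

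No scheduled step compares the ratings by arm.

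**4. Volume.** Inputs are 10 stimulation sessions per participant (Section 6.3), 16 participants per arm and 48 in total (Section 11.2). Ratings per arm = 16 × 10 = 160; total = 48 × 10 = 480, at full attendance. Questionnaires at follow-up visits (Section 14.4) are not counted.

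**5. How far the recording rule could matter (assumed rates).** The documents give no reaction rate. If a share f of sessions has a worst score of 2 or 3, then 480 × f sessions are in dispute: 480 × 0.10 = 48 at f = 10%, and 480 × 0.60 = 288 at f = 60%. All fall under Section 9.2.1; none need an AE entry on the threshold reading of Section 9.1. These are sessions, not AE counts, because the protocol does not say whether a sensation that recurs is one AE or several.

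**6. What a report without arms shows (assumed counts).** If k of 16 in one arm react and nobody elsewhere does, the arm rate is k/16 and the pooled rate is k/48.

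- k = 4: 4/16 = 25% by arm; 4/48 = 8.3% pooled.
- k = 8: 8/16 = 50% by arm; 8/48 = 16.7% pooled.

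A table by arm would remain descriptive at this size: Fisher's exact test (two-sided) gives p = 0.10 for 4 of 16 against 0 of 16, and p = 0.043 for 5 of 16 against 0 of 16.

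**The case against.** A reader might infer that stimulation reactions reach the DSMB only if it asks. The documents do not support that. The on-request item is the complete questionnaire report. Any reaction recorded as an AE is in the six-monthly AE reports, and that includes at least those above moderate.

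A reader might also infer three flatly contradictory recording rules. That too goes beyond the text. Section 9.1 does not say that lesser reactions are excluded, and its wording adds to other recording. Section 9.2.2 says where a source document is kept, not that a reaction is not an AE; Section 9.2.1 files completed AE forms in the participant's folder as well. What stands is that the three sections are not reconciled and that no link from score to AE status is given.

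Nor are the ratings lost or unreviewed. They are in REDCap (Section 14.2), weekly reports go to the investigator (Section 14.4), the medical monitor follows AEs in real time (Section 9.6), and an unexpected frequency of related events is one element of an unanticipated problem (Section 9.2.4). These safeguards count, but none is a scheduled comparison by arm.

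Two further points are fair. The questionnaires (Attachments 1 and 2) and the reporting decision tree (Attachment 10) are not in the text available and could contain the missing link; the three sections would still need to agree with it. And in a 48-person pilot, leaving the by-arm view to the DSMB's discretion is a defensible choice. Against that, the masked route already exists and the data are already entered, so scheduling it costs little.

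**Conclusion.** The point holds as a gap in recording and reporting. Sections 9.1, 9.2.1 and 9.2.2 leave open whether scores 2 and 3 become AEs, and the moderate grades on the two scales differ, so AE counts can depend on the section followed. Up to 480 post-session ratings, 160 per arm, have no scheduled comparison by arm, either at the DSMB or in the final analysis.

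The reading of the sections and the counts of 480 and 160 come from the documents, assuming full attendance. The 48 to 288 disputed sessions and the pooled-rate examples rest on assumed reaction rates and show direction only. Nothing here shows that reactions above moderate go unreported, or that the primary AHRS comparison is affected. The change should be made, but it is not critical to the trial's validity.

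**What to change.** 1. **One recording rule.** Reconcile Sections 9.1, 9.2.1 and 9.2.2 so that each questionnaire score has a stated AE status, the two severity scales are linked, and a recurring reaction is counted in a defined way. The sponsor chooses the threshold. Any threshold above mild would take out reactions that Section 9.2.1 now counts as AEs, and so remove them from the DSMB's AE reports; the amendment should say so openly.

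2. **One scheduled table, whatever the rule.** From the REDCap ratings, tabulate the worst grade per participant by masked arm (A/B/C). Put it in every six-monthly DSMB report, and by arm in the final report. Sections 9.2.2 and 9.6 would then describe the table as routine, with the on-request and for-reason routes kept for anything further.

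The cost is wording in three recording sections, a line in Section 9.6, an entry in Section 11.3 and one standard table per DSMB meeting. No new data are collected. The drawback is that the lab member not otherwise involved in the trial, who under Section 9.6 supplies the split by arm only when there is a reason, would prepare it routinely, so the allocation list is handled more often.
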